# 9. ENDPOINTS

#### 9.1 Primary endpoint

The primary endpoint is defined as the successful discontinuation of IS with maintainance of normal allograft status as assessed by liver biopsy and liver tests 12 and 24 months after IS withdrawal (operational tolerance) and stable liver tests (12, 24 and 36 months after IS withdrawal). For the purposes of validating the clinical usefulness of the tolerance biomarker, successful IS withdrawal is considered the Gold Standard. Since this outcome is strictly restricted to the IS withdrawal process and by definition cannot be observed in Arm B-, the analysis of the primary outcome will be restricted to Arms A and B+.

#### 9.2 Secondary endpoints

#### 9.2.1 The secondary clinical endpoints of the trial are defined as:

- Rejection (incidence, severity, timing, steroid resistant rejection, chronic rejection).
- Reasons for failure of IS withdrawal.
- Requirement for IS re-institution despite successful IS withdrawal on the basis of the histological criteria described in Table 5.
- Progression of graft fibrosis in tolerant participants and those on maintenance IS.
- Graft loss.
- All–cause mortality.
- Proportion of tolerant participants remaining free of rejection at 3 years post IS withdrawal.
- Renal function at 1, 2 and 3 years after enrollment.
- Change in co-morbidities associated with IS use (hypertension, cardiovascular risk profile, diabetes mellitus, hyperlipidemia, malignancy).
- Stability of the biomarker signature between baseline and last study visit.
- HrQOL changes associated with IS withdrawal.
- Pharmacoeconomic impact of IS withdrawal.
- Fibroscan:

1- To assess if drug withdrawal results in sequential changes in liver stiffness over time in patients considered tolerant.

2- To evaluate if development of an episode of rejection in patients who do not successfully discontinue immunosuppression increases liver stiffness measurements.

3- To compare changes in liver stiffness over time in patients who remain on maintenance immunosuppression and those who undergo drug weaning.

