#### 8.7 Reinstitution of IS following successful IS withdrawal

Patients who do not develop allograft dysfunction but in whom a protocol biopsy performed at 12 or 24 months after complete IS discontinuation reveales moderate inflammatory changes or other changes suggestive of progressive histological damage (as described in Table 5) will be treated with reinstitution of the baseline IS. Patients who do not exhibit any of the changes described in Table 5 but fail to meet the primary endpoint on the basis of the histological criteria defined in Table 4 will be maintained off IS until the end of the study.

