# 10.8 Liver Biopsies

Protocol liver biopsies will be performed:

- 1. At screening (to determine eligibility for study participation and to measure the transcriptional biomarker of tolerance);
- 2. 12 and 24 months after complete IS discontinuation for all recipients in Arms A and B+ who successfully withdraw IS;
- 3. 48 months after enrolment for participants on maintenance IS (Arm B-).

Patients who completely discontinue IS but require IS reinstitution on the basis of the 12-month post-withdrawal liver biopsy findings will still undergo a follow-up biopsy 24 months after IS withdrawal. In addition, "for-cause" biopsies will be performed to evaluate allograft dysfunction.

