# 12. EFFICACY ASSESSMENT

#### 12.1 Definition of efficacy outcome measures

- Allograft dysfunction: any unexplainable elevation in ALT and GGT relative to baseline and above the upper limit of normality.
- Allograft rejection: will be defined on liver biopsy according to Banff criteria. In rare cases in which it may be not feasible or safe to await the performance of a liver biopsy, episodes of severe allograft dysfunction impairment occurring during weaning that cannot be attributed to any other etiology and that rapidly respond to the empirical re-initiation of immunosuppressive drug therapy will be considered as indicative of presumed allograft rejection.
- *Histopathology of acute allograft rejection:* Acute rejection will be defined by a liver biopsy exhibiting one of the following:

a) Presence of at least 2 of the following 3 features features according to Banff criteria:
 1) predominantly mononuclear portal tract inflammation containing lymphocytes, neutrophils and eosinophils; 2) inflammatory bile duct damage; 3) venous subendothelial inflammation of portal or central veins.

b) Portal and/or lobular inflammation without bile duct damage and subendothelial inflammation provided that: 1) the inflammatory lesions were not present in the baseline (pre-weaning) biopsy; 2) they cannot be attributed to any other etiology (drug toxicity, autoimmunity, viral hepatitis); and 3) they occur in the presence of allograft dysfunction that rapidly normalizes by the re-initiation of immunosuppressive drug therapy. This takes into consideration the fact that in long-term surviving liver transplant recipients acute rejection tends to exhibit less subendothelial inflammation and greater interface and lobular activity resembling chronic hepatitis).

- *Failure of IS withdrawal*: failure to complete IS withdrawal for any reason.
- Operational tolerance: successful withdrawal of IS and maintainance of normal allograft status, as assessed by the absence of allograft dysfunction 12 months after complete IS discontinuation, and by the lack of clinically-significant changes in the liver biopsy obtained 12 months after withdrawal as described in Table 4.

Compartment	Findings				
Portal inflammation and interface	Increased portal inflammation (in comparison with a pre-weaning biopsy				
activity	sample), especially in association with histopathological evidence of				
	tissue damage manifest as: focally worsening or more prevalent				

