# Table 4. Banff Liver Allograft Pathology Working Group Criteria of Operational Tolerance Failure in Patients Off Immunosuppression

# Table 4. Banff Liver Allograft Pathology Working Group Criteria of Operational Tolerance Failure in Patients Off Immunosuppression

Compartment	Findings
Bile duct changes	New-onset biliary epithelial cell senescence changes or ductopenia when
	sampling problems and/or an alternative, non-immunological explanation
	(e.g. biliary strictures) can be reasonably excluded
Fibrosis**	Greater than 1 grade increase in fibrosis in any one compartment: (a)
	portal/periportal; (b) peri-sinusoidal; or (c) perivenular fibrosis; or new
	onset bridging fibrosis without an alternative explanation (e.g. biliary
	strictures) that is reasonably prevalent and not readily explained by a
	possible sampling error.
Arteries	Any evidence of foam cell or obliterative arteriopathy

\*Patients with underlying AIH, HCV, PBC, or PSC are excluded (25).
\*\* Fibrosis should be graded as follows (26):Portal/periportal: 0 – 3
Peri-sinusoidal: 0 – 3.
Perivenular: 0 – 3.

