#### Table 5. Follow-Up Biopsy Findings in Patients Off IS that Should Prompt Re-Institution of IS

Compartment	Findings
Portal inflammation and interface activity	Development of moderate portal inflammation or moderate interface activity in most portal tracts.
Centrizonal/perivenular inflammation	Central perivenulitis in most central veins.
Bile duct changes	New-onset biliary epithelial cell senescence changes or ductopenia when sampling problems and/or an alternative, non-immunological explanation (e.g. biliary strictures) can be reasonably excluded
Fibrosis	At least a 2 grade increase in fibrosis in any one compartment (according to Venturi et al (26)).
Arteries	Any evidence of foam cell or obliterative arteriopathy

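### The fibrosis endpoint picks its 'tolerant' group partly on fibrosis, and sets it beside a maintenance group biopsied 12 to 18 months later

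*Protocol*

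**What the plan says.** Section 9.2.1 of the protocol names two groups for histological fibrosis: "Progression of graft fibrosis in tolerant participants and those on maintenance IS". Section 8.4 identifies maintenance immunosuppression with Arm B-.

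Who counts as tolerant is defined twice. Section 12.1 requires no allograft dysfunction at 12 months and a "lack of clinically-significant changes in the liver biopsy obtained 12 months after withdrawal as described in Table 4". Section 9.1 requires normal allograft status "assessed by liver biopsy and liver tests 12 and 24 months after IS withdrawal (operational tolerance"). In Table 4 the fibrosis criterion for failure is "Greater than 1 grade increase in fibrosis in any one compartment", each compartment being graded 0 to 3, or new bridging fibrosis that is reasonably prevalent and has no other explanation. Table 5, which governs restarting immunosuppression, has "At least a 2 grade increase in fibrosis in any one compartment". Under section 8.7, participants who meet no Table 5 criterion but "fail to meet the primary endpoint on the basis of the histological criteria defined in Table 4 will be maintained off IS" until the study ends.

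Section 10.8 schedules follow-up biopsies at 12 and 24 months after complete discontinuation for those who successfully withdraw, and keeps the 24-month biopsy for those restarted because of the 12-month one. Arm B- has a single follow-up protocol biopsy, "48 months after enrolment for participants on maintenance IS (Arm B"-).

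A separate FibroScan item in section 9.2.1 is "To compare changes in liver stiffness over time in patients who remain on maintenance immunosuppression and those who undergo drug weaning". Section 10.11 takes FibroScan in all participants at screening and at months 12, 24, 36 and 48. Section 16.2 calls the secondary analyses exploratory and puts arm, biomarker status and their interaction into the models.

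**The concern.** Section 4.2 lists silent fibrosis among the main risks of withdrawal, and the first secondary objective in section 5.3 is safety. Section 4.2 also says that protocol biopsies are there to clarify the role of immunosuppression in long-term histological damage. Readers will therefore set the two fibrosis figures side by side.

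Three features make that reading unsafe. One group is defined partly by the absence of the outcome. The two groups are biopsied after different lengths of follow-up. The maintenance group consists only of biomarker-negative participants, while the tolerant group draws on biomarker-positive participants in Arm B+ and on a mix in Arm A. Section 4.2 itself faults an earlier case-control study of fibrosis in tolerant children partly because its groups differed in length of follow-up. At stake is a reassuring fibrosis result that is partly built in by the definitions and the schedule.

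**Working it through.** The protocol gives no figure on this point to reproduce. The check has four parts.

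**1. What the tolerant label removes.** On whole grades from 0 to 3, a rise of more than one grade (Table 4) is the same as a rise of at least two (Table 5).

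| Finding after withdrawal | Can be 'tolerant'? | In Arm B-? | Counted under Table 5 restart? |
|---|---|---|---|
| Rise of 0 or 1 grade, no other Table 4 finding | Yes | No | No |
| Rise of 2 or 3 grades | No | No | Yes |
| Prevalent new bridging, no 2-grade rise | No | No | Not by its fibrosis criterion |

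Under section 9.1 the observed rate of rises of two or more grades among tolerant participants is 0% at both the 12- and 24-month biopsies, whatever the true rate after withdrawal. Under section 12.1 it is 0% at 12 months only; a two-grade rise first seen at 24 months would still count.

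**2. Timing.** Weaning starts at the randomisation visit, M0 (section 10.3.3), and takes 6 to 12 months (section 5.5).

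- Last biopsy after withdrawal: 6 + 24 = M30 to 12 + 24 = M36.
- Gap to month 48: 48 − 36 = 12 to 48 − 30 = 18 months.
- Ratio of follow-up: 48/36 = 1.33 to 48/30 = 1.60.
- If only the 12-month biopsy is used: M18 to M24, a gap of 24 to 30 months.

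The step schedules in section 8.3 agree. Eight 3-week steps are 24 weeks, or 5.5 months, giving a gap of 48 − 29.5 = 18.5 months. Two drugs with three 4-week pauses take about 48 weeks, or 11.0 months, giving 48 − 35.0 = 13.0 months. Section 10.8 dates the Arm B- biopsy from enrolment, and the footnotes to Tables 2 and 3 date it from randomisation. The baseline visit is 7 weeks before M0, so this moves the gap by less than 2 months.

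**3. Size of the timing effect.** The protocol gives no progression rate, so I assume the same constant annual probability r in both groups and show a range. Cumulative progression by month t is 1 − (1 − r)^(t/12).

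| r per year | M30 | M36 | M48 | Difference due to timing |
|---|---|---|---|---|
| 5% | 12.0% | 14.3% | 18.5% | 4.2 to 6.5 points |
| 10% | 23.2% | 27.1% | 34.4% | 7.3 to 11.2 points |
| 20% | 42.8% | 48.8% | 59.0% | 10.2 to 16.2 points |

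These figures concern progression that the tolerant label still permits, such as one-grade rises. For larger rises, part 1 applies instead.

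**4. Randomised alternative.** The minimisation in section 8.2.2 includes the biomarker result, so biomarker-negative participants in Arm A (weaned) and Arm B (maintained) form a randomised contrast. With 148 randomised 1:1 and about 50% biomarker-positive (section 15), each side has 148/2 × 0.5 = 37 before dropout.

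**The case against.** The strongest reply is that section 9.2.1 names an outcome in two groups and states no test between them. Where a comparison is meant, as in the FibroScan item, the text says so, and that item covers everyone weaned. The analyses are exploratory. The arm-by-biomarker model in section 16.2 already yields biomarker-negative Arm A against Arm B-, and its mixed models for serial measures suit FibroScan at common visits. All of this stands, and it limits the weight of the point. It does not remove it: the protocol itself fixes the population, the tolerance definition and the biopsy dates, and no model can restore participants whom the endpoint leaves out.

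Three stronger readings are tempting but not supported.

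- A reader might infer that tolerant participants have no fibrosis progression by definition. Table 4 allows a one-grade rise in each of the three compartments if no other criterion is met, and section 12.1 does not use the 24-month biopsy.
- A reader might infer that progressors vanish from the trial. Rises of two or more grades appear under the endpoint on restarting immunosuppression, and they fail the primary endpoint as section 9.1 defines it.
- A reader might infer that every imbalance favours withdrawal. Nothing in the protocol shows how biomarker status relates to fibrosis, so that direction is unknown. Withdrawn participants also have two follow-up biopsies against one. Section 4.1.1 cites sampling error of up to 20%, so counting any positive reading could work against withdrawal.

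**Conclusion.** The point holds as a flaw in how one exploratory safety endpoint is defined. Selection on the outcome follows directly from the protocol's text: rises of two or more grades and prevalent new bridging are excluded from the tolerant group, at 12 months or at both 12 and 24 months depending on which definition applies. The 12 to 18 month difference in biopsy timing follows from the stated schedule. Its effect, about 4 to 16 percentage points in favour of the tolerant group, rests on an assumed equal and constant progression rate of 5 to 20% a year. The contrast with Arm B- is also not randomised, with a bias of unknown direction. The primary analysis is not affected.

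**What to change.** - Reconcile the definitions of operational tolerance in sections 9.1 and 12.1.
- Define the histological fibrosis endpoint in all Arm A and B+ participants with a 12- or 24-month post-withdrawal biopsy, whatever the Table 4 or Table 5 result and including those restarted on immunosuppression. A tolerant-only summary can stay as a labelled subset.
- Account for time from the baseline biopsy whenever this is set beside Arm B-. A simple grade change per year would treat an ordinal 0 to 3 scale as linear, so it should not be the only summary.
- State that participants who fail weaning have no scheduled follow-up biopsy, so the histological comparison stays partial and non-randomised.
- For the third FibroScan item, name biomarker-negative Arm A against Arm B- as the main comparison of weaning with maintenance. It is already estimable from the section 16.2 model.

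The cost is wording only, with no added biopsies or visits. The limits are small groups, about 37 against 37, and the fact that stiffness measures fibrosis only indirectly.

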#### 9.2.2 The secondary mechanistic endpoints of the trial are:

• Intra-hepatic and systemic iron parameters.

- Time post-transplant, age, sex and type of IS.
- Markers of immune-exhaustion in blood and liver tissue.
- Gut microbiome profile.
- Blood and intra-hepatic lymphocyte subsets (including regulatory T cells).
- Development of anti-HLA antibodies (before and after initiation of IS withdrawal).

### 10. ASSESSMENTS AND FOLLOW-UP

#### 10.1 Evaluation of eligibility

All participants meeting the inclusion criteria will be identified from the local transplant clinics. At the start of the trial, the entire population of transplant clinic attendees who are >3 years post-transplantation are potentially eligible for recruitment. On subsequent screening rounds, participants who reach 3 years post-transplantation after the start of the trial will become eligible.

#### 10.2 Informed consent

Eligible participants will be approached at a routine clinic appointment by a trial investigator or research nurse, and given printed and verbal information about the trial. They will have the opportunity to return for a second consultation within a few days to give informed consent for recruitment into the study.

### 10.3 Timing of visits

### 10.3.1 Baseline visit

Consenting participants will have the following baseline assessments completed during their visit:

- Informed consent
- Physical exam (including height and weight measurement)
- Vital signs;
- Gender
- Ethnicity
- Date of birth
- Pre- and post-transplant medical history.
- Urine or blood βhCG (females)
- HLA type and that of donor liver (if available)
- Viral serology
- Autoantibody panel (ANA, AMA, SMA, LKM, quantitative IgG)
- IS drug 12-hour trough levels (as appropriate).
- MDRD eGFR

- Biochemistry panel (including creatinine, urea, electrolytes (sodium, potassium), and glucose).
- Full blood count (FBC) (including differential WBC count).
- Liver function tests (LFT) (including ALT, AST, GGT, alkaline phosphatase, total bilirubin (total and conjugated fraction at baseline visit)).
- Review of inclusion & exclusion criteria
- Concomitant medication

# 10.3.2 Screening Visit (3 weeks + /- 1 week)

The following assessments will be performed and recorded.

- Review of inclusion and exclusion criteria.
- Physical examination and vital signs
- Full blood count (FBC)
- Biochemistry panel
- Liver function tests (LFT)
- Baseline liver biopsy (see section 10.8)
- Blood draw for mechanistic studies
- Gut microbiome (stool)
- Diagnosis of the biomarker test
- Advesrse event (AE) since time of consent.
- Concomitant medications

### 10.3.3 Randomisation Visit (4-6 weeks post liver biopsy)

Subjects identified as eligible for the clinical trial based on all screening procedures including liver biopsy results will attend a Randomisastion Visit that needs to occur within 6 weeks of performing the biopsy, and within 2 weeks of receiving the email from LIFT with the randomisation results In participants randomised to IS withdrawal the Randomisation Visit will mark the beginning of the IS withdrawal protocol.

- Review of inclusion / exclusion criteria
- Liver function tests (LFT)
- Blood draw for mechanistic studies
- Metabolic panel (HbA1c, fasting glucose, fasting total colesterol, LDL, HDL)
- HLA antibodies
- Treatment-related diseases history infection (CMV, fungal, other), biliary conditions, type II diabetes, kidney failure (possibly due to CNI), PTLD, cancer.
- Randomisation
- Adverse events
- Concomitant medications
- HrQOL assessment

Please note: Start decreasing the IS doses as per section 8.3 of this protocol.

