#### 6.3 Patient withdrawal criteria

Participants may be prematurely terminated from the study for the following reasons:

- 1. the participant elects to withdraw consent from all future study activities, including follow-up;
- 2. the participant is "lost to follow-up";
- 3. the participant dies;
- 4. any participant who fails screening and is deemed ineligible to initiate IS withdrawal;
- 5. pregnancy.

Participants have the right to voluntarily discontinue study treatment or withdraw from the study at any time for any reason without any consequences

The investigator has the right to discontinue a participant from study treatment or withdraw a participant from the study at any time if it is in the best interest of the participant.

Any medical condition that the investigator or sponsor determines may jeopardize the participant's safety if she or he continues receiving the study treatment. Screening failures will not be randomized and will not count towards the final sample size.

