#### 8.2.1 Randomisation Procedure

A patient identification number (PIN) will be generated by registering the patient on the MACRO eCRF system (InferMed Macro), after consent has been signed. This unique PIN will be recorded on all source data worksheets and used to identify the patient throughout the study. Authorised site staff will be allocated a username and password for the randomization system. Once a patient is consented, all baseline data collected and eligibility confirmed, the staff member will log into the randomization system (www.ctu.co.uk) and click 'randomisation – advanced' and select LIFT and

enter the participants details (including MACRO PIN). The 'help' section of the system has video demonstrations to aid new staff in using the system. Once randomized, the system automatically generates confirmation emails to key staff, with or without treatment allocation information, depending on their role in the study. Participants that withdraw will not be replaced; levels of attrition have formed part of the sample size calculation to accommodate this.

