# 16. STATISTICAL ANALYSIS

#### 16.1 Primary Analysis

To test for superiority of arm B+, compared to arm A, we will compare the proportion of successfully weaned participants in each arm using generalized linear mixed models (GLMM) (logistic regression) with random effects for study centre, as a factor used in the minimisation procedure. Potential confounding will be examined, as part of sensitivity analysis, for the following covariates: (study centre, age at randomization, time from transplantation at randomization, a binary indicator of whether the participant was receiving a second drug at baseline). The primary outcome will be analysed per Intention-to-Treat, i.e. participants allocated to arms A or B+ who do not start the weaning protocol or initiate weaning but do not complete it, will be treated as 'failures'. To ultimately validate the clinical utility of the biomarker, 2 further conditions will need to be met: 1) the confidence interval of the proportion of successes in arm B+ should include 0.80 and exclude 0.50; and 2) the confidence interval of the test's sensitivity as estimated in arm A should include 0.70 and exclude 0.50.

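### The last eligibility review and liver tests fall at a visit held after the randomisation result has reached the site, contrary to the order set in section 8.2.1

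*Protocol*

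**What the plan says.** Section 8.2.1 sets the order: "Once a patient is consented, all baseline data collected and eligibility confirmed, the staff member will log into the randomization system". Section 6.3 adds that screening failures are not randomised and do not count towards the sample size.

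Section 10.3.3 (Randomisation Visit) opens in the same spirit: "Subjects identified as eligible for the clinical trial based on all screening procedures including liver biopsy results will attend" the visit. It then requires the visit to fall within 6 weeks of the biopsy and "within 2 weeks of receiving the email from LIFT with the randomisation results". The procedures listed for the visit include "Review of inclusion / exclusion criteria", liver function tests and randomisation itself. It is also where weaning starts: "In participants randomised to IS withdrawal the Randomisation Visit will mark the beginning of the IS withdrawal protocol". Table 2 (section 11.1) likewise places both the inclusion/exclusion review and randomisation at M0.

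Two other passages bear on a participant who fails that review. One of the grounds for termination in section 6.3 is "any participant who fails screening and is deemed ineligible to initiate IS withdrawal". Section 16.1 treats as failures, under intention to treat, "participants allocated to arms A or B+ who do not start the weaning protocol", together with those who start but do not finish.

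**The concern.** If the result is emailed first and the visit follows up to two weeks later, the last eligibility check is made with the allocation known. Some of the criteria call for judgement. Exclusion 13 rests on the principal investigator's opinion of whether a medical condition would interfere with safe completion, and exclusion 12 on whether the participant can comply with study treatment. A doubtful participant could be held back if due to wean and retained if due to stay on maintenance.

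The exposure is not balanced between the randomised arms. Everyone in Arm A faces a decision to start weaning, whereas in Arm B only the biomarker-positive participants do. The comparisons of the two strategies as randomised (safety, cost, quality of life) are therefore the ones at risk of selective non-start or withdrawal. In the primary comparison, participants who fail the re-check after allocation count as failures for a reason that may have nothing to do with tolerance.

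**Working it through.** **1. Sequence, section by section**

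| Source | Order stated or implied |
|---|---|
| 8.1, 8.2.2 | Subjects found eligible → biomarker test → minimisation using the biomarker result |
| 8.2.1 | Baseline data and eligibility complete → randomisation → confirmation emails |
| 10.3.3, timing sentence | Randomisation result emailed → visit within 2 weeks |
| 10.3.3, procedure list; Table 2, M0 | Eligibility review, liver tests and randomisation all at the visit |

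Randomisation cannot both precede the visit by up to two weeks and take place at it. Only the timing sentence puts the review after the result, but it is explicit.

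**2. Is the M0 review a first decision or a repeat?** A repeat. The criteria are reviewed at the baseline visit (10.3.1) and again at screening (10.3.2: "Review of inclusion and exclusion criteria"). The ALT and bilirubin criterion in 6.1 is tied to the screening visit.

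**3. Are the M0 liver tests needed before weaning?** Sometimes. Section 8.3 asks for at least 3 weeks of stable liver function shown by two laboratory exams. Table 2 puts baseline at −7 weeks and screening at −4 weeks, 3 weeks apart, which can meet this. The screening window in 10.3.2 is 3 weeks ± 1 week, so the gap may be only 2 weeks. The M0 test may then be the one that completes the requirement.

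**4. Who is exposed?** Of 148 participants randomised 1:1, 74 are in each arm. With 50% biomarker-positive (section 15), Arm B splits into about 37 B+ and 37 B−. A decision to start weaning faces 74 of 74 in Arm A and about 37 of 74 in Arm B, 111 in all.

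**5. The plan's own sample size.** With unpooled variance, two-sided 5% (sidedness is not stated), 90% power and A:B+ of 2:1:

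n_A = (1.960 + 1.282)² × (0.25 + 0.16/0.5) / 0.30² = 66.5, so 67.

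Then 1.5 × 66.5 = 99.8 (stated 100), 2 × 67 = 134 (stated 134), and 134 × 1.10 = 147.4, so 148 (stated 148). The stated figures reproduce, and the sequencing problem does not alter them.

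**6. Illustration of dilution.** The documents give no rate of failing the M0 review. Assume a fraction f of 5-10%, equal in both weaning groups, all scored as failures under 16.1:

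- Number affected: 111 × 0.05 = 5.6 to 111 × 0.10 = 11.1, about 6 to 11.
- B+: 0.80 × 0.95 = 0.76; 0.80 × 0.90 = 0.72.
- Arm A: 0.50 × 0.95 = 0.475; 0.50 × 0.90 = 0.45.

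Power = Φ(difference / √[p_A(1−p_A)/74 + p_B(1−p_B)/37] − 1.960), with no other dropout:

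| f | Arm A | B+ | Difference / standard error | Power |
|---|---|---|---|---|
| 0 | 0.500 | 0.80 | 0.300/0.0878 = 3.42 | 92.8% |
| 5% | 0.475 | 0.76 | 0.285/0.0911 = 3.13 | 87.9% |
| 10% | 0.450 | 0.72 | 0.270/0.0938 = 2.88 | 82.1% |

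A check held before allocation would screen these people out, and others could be randomised in their place. Power would then stay at the f = 0 value.

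**7. Does this alone breach the validation rule in 16.1?** That rule asks for the B+ confidence interval to include 0.80 and exclude 0.50. With 37 in B+, 27 successes (73%) give an exact 95% interval of 0.56 to 0.86, and 28 (76%) give 0.59 to 0.88. Both satisfy the rule.

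**The case against.** The strongest reply is that eligibility is already decided before allocation, several times over. It is reviewed at baseline and at screening, the histology is read by a central pathologist, section 8.2.1 requires confirmation before login, and only subjects already found eligible attend the Randomisation Visit. This stands. A reader might infer that eligibility is first decided with the allocation known, and the documents do not support that. What they permit is a repeat review at that point.

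A reader might also infer that the same people are both terminated under 6.3 and scored as failures under 16.1. The full wording of the fourth ground in 6.3 concerns participants who fail screening, and such people are not randomised; 16.1 concerns participants already allocated. No section drops an allocated participant from the primary analysis. What remains is that no passage says what the M0 review is for, or whether an allocated participant who fails it leaves the study or stays in follow-up.

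Thirdly, section 5.4 blinds weaning participants and their physicians to the biomarker result, so there is little scope to treat A and B+ differently. This too stands, and it is why the primary effect is dilution and not differential bias. The blinding does not conceal whether a participant is to be weaned or maintained. Role-dependent emails (8.2.1) do not conceal it either, since dose reduction begins at the visit and B− participants know their status.

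Finally, the secondary analyses are labelled exploratory in 16.2, and the timing sentence may be loose drafting. Both are fair. They lower the stakes, but a site following that sentence as written would still do the review after the result.

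**Conclusion.** The point holds in limited form. Sections 8.2.1, 10.3.3 and Table 2 contradict one another on when randomisation occurs. Under the explicit timing sentence, a partly discretionary eligibility review is repeated when wean-versus-maintain is known. The secondary A-versus-B comparisons are open to selective non-start or withdrawal, because about 111 of 148 participants face a weaning decision and they are unevenly spread across the arms. The documents allow no estimate of how large that effect would be.

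For the primary comparison the consequence is mainly dilution. At an assumed 5-10% failing the re-check equally in both groups, power falls from 92.8% to 87.9-82.1% with 74 versus 37 analysed. The loss scales with the assumed rate and disappears if nobody fails. It would be too strong to say that a biomarker with a true PPV of 0.80 would then fail validation. The observed proportion would sit below the 0.80 named in section 15, but the interval rule in 16.1 could still be met. The correction is worth making because it is cheap and removes the problem at source.

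**What to change.** - Reconcile 8.2.1, 10.3.3 and Table 2 to one sequence: the final inclusion/exclusion review and the repeat liver tests are completed and entered before the site requests randomisation, and the allocation is released only after that entry.
- In 6.3, state that the fourth ground for termination applies only before randomisation.
- State that a participant who cannot start weaning after allocation stays in follow-up in the allocated group and is analysed as 16.1 already provides.

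This reorders existing steps and adds no procedure. The cost is that weaning may start a few days later while the liver tests are read. The revised sequence also has to fit the 6-week limit after biopsy in 10.3.3.
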